6.0 STRATIFICATION FACTORS

Randomization will be dynamically balanced according to sex (female vs. male) and ostomy status (permanent ostomy vs. anastomosis).

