Motivation is measured using a 10-item scale assessing motivation to change dietary behaviors in rectal cancer survivors from the **S1820** Reasons for Managing Bowel Health form. It was developed internally, based on the Reasons for Quitting (Intrinsic and Extrinsic Motivation) scale.⁷³ Items are scored on a 5-point Likert scale, from 0 ("Not true at all") to 4 ("Extremely true"). The score is calculated by summing all responses; higher scores indicate higher motivation. Motivation is assessed prior to Step 1 registration (baseline), and at Week 18 and Week 26.

f. Self-Efficacy

Self-efficacy is measured using the Patient-Reported Outcomes Measurement Information System (PROMIS) Self-Efficacy for Managing Symptoms – Short Form 4a, a validated instrument that measures confidence in one's ability to successfully perform specific tasks or behaviors related to self-efficacy for managing symptoms. The four items are scored on a 5-point Likert scale, from 1 ("I am not at all confident") to 5 ("I am very confident"). The overall score is calculated by summing all responses and converting to a PROMIS T-score; higher scores indicate greater self-efficacy.⁷⁴ Self-efficacy is assessed prior to Step 1 registration (baseline), Week 18 and Week 26.

g. Positive and Negative Affect

Affect is measured using the 10-item International Positive and Negative Affect Schedule Short Form (I-PANAS-SF), a validated instrument comprised of two mood scales: Positive Affect (PA) and Negative Affect (NA).^{75, 76} The scores are calculated by summing the responses for positive and negative affect items separately. Scores range from 5 to 25, with higher scores on these scales indicate greater positive affect or negative affect, respectively. Affect is assessed prior to Step 1 registration (baseline), Week 18 and Week 26.

h. Feasibility, adherence, retention, and acceptability

Feasibility, adherence, retention, and acceptability are descriptive measures that will be used to characterize the successfulness of the intervention in this pilot trial and guide the study team in preparing for the Phase III trial. These measures are evaluated based on data obtained throughout the study period.

Feasibility is measured by the percentage of patients who successfully complete ("pass") the run-in period and are randomized. Successful completion is defined as meeting all five of the following measures:

1. Patient answers the telephone calls from trained staff at the University of Arizona.

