11.2 Primary Endpoint Analyses

The analysis of the primary endpoint will be conducted in all eligible patients randomized to the study with 18-week BFI data regardless of adherence to the coaching calls, according to a modified intention-to-treat principle. Study arm differences in BFI at 18 weeks will be assessed by a linear regression model as a function of randomization assignment, BFI baseline value, and stratification factors. Due to the low safety risks of this study, we will not perform an interim futility analysis.

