11.3 Other Analyses

Given the modest size of this trial, the exploratory endpoint analyses are considered hypothesis-generating. Study arm differences in BFI at 26 weeks will be assessed by a linear regression model as a function of randomization assignment, BFI baseline value, and stratification factors. Other continuous exploratory outcomes at both 18 and 26 weeks (BFI subscales, LARS, quality of life, dietary quality, motivation, self-efficacy, and positive/negative affect) will be assessed by a repeated measures linear regression model as a function of

randomization assignment, baseline value of the outcome, stratification factors, and visit. Robust standard errors will be estimated via generalized estimating equations to adjust for correlation between repeated outcome measures. The dependent variables will be transformed to approximate normality as appropriate.

Accrual rates and feasibility will be summarized. Study arm differences in adherence and retention will be assessed by chi square tests. Study program acceptability will be compared across arms via t-test.

Although the sample size provides limited statistical power for subgroup analyses, we will explore the impact of sex by reanalyzing all outcomes according to sex as feasible. The potential for differential intervention effects according to sex on the primary endpoint will also be considered.

To assess the sensitivity of intervention effects to the potential confounding factor of site-based symptom management, additional exploratory BFI models will adjust for such treatments used by participants at baseline and during the intervention.

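### Adherence, retention and acceptability are compared without the factors used to balance randomization; if those factors are prognostic, the tests are mildly conservative

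*Combined protocol and SAP*

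**What the plan says.** Section 6.0 balances randomization dynamically on two factors, sex and ostomy status. It does not give the algorithm or any random element.

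Section 11.2 analyses the primary endpoint with a "linear regression model as a function of randomization assignment, BFI baseline value, and stratification factors". Section 11.3 uses the same form of model for the BFI at 26 weeks. It analyses the other continuous exploratory outcomes by repeated measures regression on "randomization assignment, baseline value of the outcome, stratification factors, and visit".

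Three measures are treated differently. Section 11.3 states "Study arm differences in adherence and retention will be assessed by chi square tests" and "Study program acceptability will be compared across arms via t-test". It mentions no adjustment or stratification for them and gives no reason for the exception. It sets no significance level or power target for these comparisons.

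On their status, Section 10.2h says "Feasibility, adherence, retention, and acceptability are descriptive measures that will be used to characterize the successfulness of the intervention in this pilot trial", and Section 11.3 says that "the exploratory endpoint analyses are considered hypothesis-generating".

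**The concern.** When allocation is forced to be balanced on a factor that predicts the outcome, the difference between arms varies less than it would under simple randomization. A test that ignores the factor still counts the between-stratum variation as noise. Its standard error is then too large, its true level falls below nominal, and some power is lost. The plan avoids this for the BFI and the other continuous outcomes, but not for these three.

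The protocol gives a reason to think that sex might matter here. Section 2.0 says that men may respond differently to lifestyle programmes and lists lack of interest and perceived unsuitability among the reasons, both of which bear on uptake and acceptance.

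What is at stake is modest: how precisely the trial describes arm differences in three measures that are meant to guide preparation of a Phase III trial.

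**Working it through.** **The plan's own figures.** No figure is given for these three comparisons. The stated sample size does reproduce: 37 per arm, effect 0.5 SD, one-sided alpha 0.1 gives 80.4% power (noncentral t), and 74/(0.93 × 0.85) = 93.6, rounded up to 94.

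**Inputs.** From the documents: 94 randomized (47 per arm), 74 evaluable, and 58 women and 36 men in the planned enrolment table (29 and 18 per arm). Assumed: nominal two-sided 5%, an ostomy share of about 30%, and the strength of prognosis, which is varied.

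**Acceptability, closed form.** If strata are balanced and explain a share R² of the variance, the t-test standard error is too large by 1/√(1 − R²), and the true level is 2 × [1 − Φ(1.96/√(1 − R²))].

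- R² = 0.04: 1/√0.96 = 1.021; level 2 × [1 − Φ(2.000)] = 4.5%.
- R² = 0.10: 1/√0.90 = 1.054; level 2 × [1 − Φ(2.066)] = 3.9%.

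**Adherence and retention, closed form.** Assume per-arm strata of 20, 9, 12 and 6 (women without and with ostomy, then men without and with ostomy). Compare the pooled variance p(1 − p) with the average within-stratum variance.

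- Strong prognosis, 90/85/60/55%: p = 36.15/47 = 0.769, pooled variance 0.1776, within-stratum variance 7.3125/47 = 0.1556, ratio 0.876. Level 2 × [1 − Φ(1.96/√0.876)] = 3.6%.
- Moderate prognosis, 85/80/70/65%: p = 36.5/47 = 0.777, pooled variance 0.1735, within-stratum variance 7.875/47 = 0.1676, ratio 0.966. Level 4.6%.

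**Power, same strata, by simulation** (chi-square, then Cochran-Mantel-Haenszel, CMH):

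| Prognosis | One arm lower, OR 0.4 | One arm higher, OR 2.5 |
|---|---|---|
| Strong | 41% vs 46% | 31% vs 34% |
| Moderate | 50% vs 51% | 35% vs 35% |

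The gain from stratifying is about 2.5 to 5.6 points under strong prognosis and −0.4 to +1.2 points under moderate prognosis. If the factors are not prognostic, about one point is lost.

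**Check with dynamic balancing.** The closed forms assume exact balance in every joint stratum, which Section 6.0 does not promise. Minimization on the two margins was therefore simulated with an assumed 0.8 biased coin and 30% ostomy share (20,000 null and 10,000 alternative replicates).

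| Measure and prognosis per factor | True level, unadjusted vs adjusted | Power, unadjusted vs adjusted |
|---|---|---|
| Binary (N = 94, log OR 1.2), none | 5.1% vs 4.9% | 55.6% vs 53.8% |
| Binary, OR 2 | 4.8% vs 4.9% | 48.7% vs 47.9% |
| Binary, OR 4 | 4.0% vs 4.9% | 44.0% vs 45.5% |
| Acceptability (N = 74, 0.5 SD), none | 5.0% vs 5.0% | 55.6% vs 55.5% |
| Acceptability, 0.3 SD (R² about 4%) | 4.6% vs 5.0% | 54.6% vs 56.0% |
| Acceptability, 0.5 SD (R² about 10%) | 4.1% vs 5.1% | 52.2% vs 55.9% |
| Acceptability, 0.8 SD (R² about 22%) | 2.7% vs 4.8% | 46.1% vs 56.4% |

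The pattern is the same, slightly weaker for the binary measures. The unadjusted tests never exceed nominal level beyond simulation error.

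**The case against.** The strongest answer is that nothing shows these factors to be prognostic here. Section 2.0 says only that men may respond differently, calls the evidence for telephone counselling limited, and notes a lack of data on sex differences in uptake. This stands: the effect is conditional. A reader might infer that the p-values are certainly wrong, and the documents do not support that.

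Second, the measures are descriptive and hypothesis-generating, with no significance level set. This also stands, and it keeps the point minor. A reader might go further and infer that testing contradicts the descriptive label, or that intervals have been ruled out. Neither follows: a supplementary test is compatible with description, and nothing in Section 10.2h excludes reporting intervals.

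Third, the power gain for the binary measures is small and depends on the scenario. The five-point gain needs odds ratios of about 4.6 to 6 between women and men within ostomy strata (0.85 vs 0.55 and 0.90 vs 0.60) and an intervention effect that lowers adherence. This stands. For adherence and retention the case rests mainly on consistency and valid error estimates.

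Fourth, Section 11.3 already plans to reanalyse outcomes by sex as feasible. That is a subgroup description and does not replace an adjusted comparison of the arms; it also leaves out ostomy status.

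A reader might also infer that acceptability is measured only in patients who continue the calls. The documents do not support that: Section 7.10 follows all randomized patients for 26 weeks, and Section 10.2h measures acceptability in all participants.

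**Conclusion.** The inconsistency is real and minor. These three comparisons ignore the balancing factors, while the other specified between-arm outcome models include them. If sex or ostomy status is prognostic, the unadjusted tests are conservative to the extent shown in the working. The loss is material only for acceptability under strong prognosis: about 10 points of power at 0.8 SD per factor, against about 1 to 4 points at 0.3 to 0.5 SD.

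These sizes rest on the assumed ostomy share, the allocation algorithm, the two-sided 5% level and the assumed strength of prognosis, none of which the documents give. A reader might infer that ignoring the factors raises the false-positive rate or weakens the primary result. It does neither: the error runs in the conservative direction, the primary model already adjusts, and the sample size does not depend on these tests.

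**What to change.** Amend Section 11.3 as follows.

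- Compare acceptability between arms by linear regression on arm, sex and ostomy status, and report the adjusted difference with its confidence interval.
- Compare adherence and retention by a Cochran-Mantel-Haenszel analysis stratified by sex and ostomy status, and report the stratified risk difference with its confidence interval.
- State in advance how sparse strata will be collapsed.

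The cost is a few lines of wording and code, with no new data. The downsides are that the smallest strata (6 per arm under the split assumed here) may need collapsing, and that about one point of power, or up to two in the minimization simulation, may be lost on the binary measures if the factors are not prognostic.

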11.4 Accrual

Based on a survey of sites represented at the SWOG Survivorship Committee, we estimate availability of at least 600 potentially eligible patients each year. If 75% of eligible patients registered to Step 1 will be randomized to Step 2, we anticipate registering 126 patients to Step 1. Thus, we have set a target of registering 5-6 patients per month to Step 1 to allow for complete enrollment to Step 2 (randomization) in approximately 2 years.

11.5 Data and Safety Monitoring

A Data and Safety Monitoring Committee will oversee the conduct of the study. The Committee consists of four members from outside of SWOG, 3 SWOG members, 3 non-voting representatives from the National Cancer Institute (NCI), and the Group Statistician (non-voting). The members of this Committee will receive confidential reports every 6 months from the SWOG Statistics and Data Management Center, including CTCAE-graded symptom data, and will meet at the Group's bi-annual meetings as necessary. The Committee will be responsible for decisions regarding possible termination and/or early reporting of the study, based on accrual and feasibility.

12.0 DISCIPLINE REVIEW

There is no discipline review for this study.

13.0 REGISTRATION GUIDELINES

13.1 Registration Timing

For Step 1 registration: Patients must be registered within 7 days after consent and completion of baseline questionnaires. This will allow for timely completion of the run-in period at a maximum of 40 days. (See [Section 18.5](#) for COVID-19-related exception.)

For Step 2 registration (randomization): Patients must be registered within 5 days after notification of run-in completion from the University of Arizona. (See [Section 18.5](#) for COVID-19-related exception.)

13.2 CTEP Investigator Registration Procedures

Food and Drug Administration (FDA) regulations and National Cancer Institute (NCI) policy require all individuals contributing to NCI-sponsored trials to register and to renew their registration annually. To register, all individuals must obtain a Cancer Therapy Evaluation Program (CTEP) Identity and Access Management (IAM) account at <https://ctepcore.nci.nih.gov/iam>. In addition, persons with a registration type of Investigator (IVR), Non-Physician Investigator (NPIVR), or Associate Plus (AP) (i.e., clinical site staff requiring write access to OPEN, Rave, or acting as a primary site contact) must complete their annual registration using CTEP's web-based Registration and Credential Repository (RCR) at <https://ctepcore.nci.nih.gov/rrc>.

RCR utilizes five person registration types.

- IVR — MD, DO, or international equivalent;
- NPIVR — advanced practice providers (e.g., NP or PA) or graduate level researchers (e.g., PhD);
- AP — clinical site staff (e.g., RN or CRA) with data entry access to CTSU applications (e.g., Roster Update Management System (RUMS), OPEN, Rave,);
- Associate (A) — other clinical site staff involved in the conduct of NCI-sponsored trials; and
- Associate Basic (AB) — individuals (e.g., pharmaceutical company employees) with limited access to NCI-supported systems.

RCR requires the following registration documents:

Documentation Required	IVR	NPIVR	AP	A	AB
------------------------	-----	-------	----	---	----

FDA Form 1572

<https://ctep.cancer.gov/investigatorResources/default.htm>. For questions, please contact the **RCR Help Desk** by email at [contact].

a. CTSU Registration Procedures

This study is supported by the NCI Cancer Trials Support Unit (CTSU).

1. **IRB Approval:**

For CTEP and Division of Cancer Prevention (DCP) studies open to the National Clinical Trials Network (NCTN) and NCI Community Oncology Research Program (NCORP) Research Bases after March 1, 2019, all U.S.-based sites must be members of the NCI Central Institutional Review Board (NCI CIRB). In addition, U.S.-based sites must accept the NCI CIRB review to activate new studies at the site after March 1, 2019. Local IRB review will continue to be accepted for studies that are not reviewed by the CIRB, or if the study was previously open at the site under the local IRB. International sites should continue to submit Research Ethics Board (REB) approval to the CTSU Regulatory Office following country-specific regulations.

Sites participating with the NCI CIRB must submit the Study Specific Worksheet for Local Context (SSW) to the CIRB using IRBManager to indicate their intent to open the study locally. The NCI CIRB's approval of the SSW is automatically communicated to the CTSU Regulatory Office, but sites are required to contact the CTSU Regulatory Office at [contact] to establish site preferences for applying NCI CIRB approvals across their Signatory Network. Site preferences can be set at the network or protocol level. Questions about establishing site preferences can be addressed to the CTSU Regulatory Office by emailing the email address above or calling [name].

2. **Downloading Site Registration Documents:**

Download the site registration forms from the protocol-specific page located on the CTSU members' website. Permission to view and download this protocol and its supporting documents is restricted based on person and site roster assignment. To participate, the institution and its associated investigators and staff must be associated with the LPO or a PO on the protocol.

- Log on to the CTSU members' website (<https://www.ctsu.org>) using your CTEP-IAM username and password;
- Click on *Protocols* in the upper left of your screen
 - Enter the protocol number in the search field at the top of the protocol tree, or
 - Click on the By Lead Organization folder to expand, then select *[Corresponding Organization]*, and protocol number *[NCI Protocol #]*;
- Click on *Documents*, select *Site Registration*, and download and complete the forms provided. (Note: For sites under the CIRB initiative, IRB data will load automatically to the CTSU as described above.)

3. **Requirements for S1820 Site Registration:**

- IRB approval (For sites not participating via the NCI CIRB; local IRB documentation, an IRB-signed CTSU IRB Certification Form, Protocol of Human Subjects Assurance Identification/IRB Certification/Declaration of Exemption Form, or combination is accepted).
- **Study Site Staff Training Requirement:** Sites interested in participating in S1820 will need to have at least one designated staff member complete a training session. Training must be completed

prior to enrollment of any patients. Training requirements and content for can be obtained in the following methods:

- A 2-hour training session will be held at select semi-annual meetings (April and October).
- Web-based training will be available and will require online access and speakers. To enroll in the training, sites must register for the training at <https://www.swog.org/required-s1820-training> .
- A list of study staff training including name, site, contact information and date of training completion will be maintained by the Study Chair. The designated trained staff at each SWOG site will also be invited to participate in monthly study telephone conference calls, which may include training updates.
- If the designated trained staff leaves the SWOG institution, sites will need to provide access and completion of training for all new personnel participating in this protocol prior to any new enrollment of patients.

4. Submitting Regulatory Documents:

Submit required forms and documents to the CTSU Regulatory Office via the Regulatory Submission Portal on the CTSU website.

To access the Regulatory Submission Portal log on to the CTSU members' website → Regulatory → Regulatory Submission.

Institutions with patients waiting that are unable to use the Regulatory Submission Portal should alert the CTSU Regulatory Office immediately at [name] in order to receive further instruction and support.

13.3 OPEN Registration Requirements

The Oncology Patient Enrollment Network (OPEN) is a web-based registration system available on a 24/7 basis. OPEN is integrated with CTSU regulatory and roster data and with the Lead Protocol Organization (LPOs) registration/randomization systems or Theradex Interactive Web Response System (IWRS) for retrieval of patient registration/randomization assignment. OPEN will populate the patient enrollment data in NCI's clinical data management system, Medidata Rave.

Requirements for OPEN access:

- A valid CTEP-IAM account;
- To perform enrollments or request slot reservations: Be on a LPO roster, ECTCN Corresponding roster, or PO roster with the role of Registrar. Registrars must hold a minimum of an AP registration type;
- If a Delegation of Tasks Log (DTL) is required for the study, the registrar(s) must hold the OPEN Registrar task on the DTL for the site; and
- Have an approved site registration for a protocol prior to patient enrollment.

To assign an Investigator (IVR) or Non-Physician Investigator (NPIVR) as the treating, crediting, consenting, drug shipment (IVR only), or receiving investigator for a patient transfer in OPEN, the IVR or NPIVR must list the IRB number used on the site's IRB approval on their Form FDA 1572 in RCR. If a DTL is required for the study, the IVR or NPIVR must be assigned the appropriate OPEN-related tasks on the DTL.

Prior to accessing OPEN, site staff should verify the following:

- Patient has met all eligibility criteria within the protocol stated timeframes; and
- All patients have signed an appropriate consent form and HIPAA authorization form (if applicable).

Note: The OPEN system will provide the site with a printable confirmation of registration and treatment information. Please print this confirmation for your records.

Access OPEN at <https://open.ctsu.org> or from the OPEN link on the CTSU members' website. Further instructional information is in the OPEN section of the CTSU website at <https://www.ctsu.org> or <https://open.ctsu.org>. For any additional questions, contact the CTSU Help Desk at [name] or [contact].

13.4 Registration Procedures

- a. All site staff will use OPEN to enroll patients to this study. OPEN is integrated with the CTSU Enterprise System for regulatory and roster data and, upon enrollment, initializes the patient in the Rave® database. OPEN can be accessed at <https://open.ctsu.org>, from the OPEN tab on the CTSU members' side of the website at <https://www.ctsu.org>, or from the OPEN Patient Registration link on the SWOG CRA Workbench.
- b. Prior to accessing OPEN site staff should verify the following:
 - All eligibility criteria have been met within the protocol stated timeframes and the affirmation of eligibility on the Registration Worksheet has been signed by the registering investigator or another investigator designate. Site staff should refer to [Section 5.0](#) to verify eligibility.
 - All patients have signed an appropriate consent form and HIPAA authorization form (if applicable).
- c. The OPEN system will provide the site with a printable confirmation of registration and intervention information. Please print this confirmation for your records.
- d. Further instructional information is provided on the OPEN tab on the CTSU members' side of the website at <https://www.ctsu.org> or at <https://open.ctsu.org>. For any additional questions contact the CTSU Help Desk at [name] or [contact].

13.5 Exceptions to SWOG registration policies will not be permitted.

- a. Patients must meet all eligibility requirements.
- b. Institutions must be identified as approved for registration.
- c. Registrations may not be cancelled.

